10.2 Analyses of vital signs and body weight

Blood pressure (systolic and diastolic), pulse rate, and body weight will be analyzed. The time-points for evaluation of vital signs and body weight are taken to be the baseline, weeks 4, 16, 28, 40, and 50 after administration initiation, and the final evaluation time (weeks 51 to 52, or at discontinuation of the treatment period or tapering period).

- 1) With respect to blood pressure (systolic and diastolic), pulse rate, and body weight, summary statistics of observed values at each evaluation time-point and changes from baseline will be calculated.
- 2) For consecutive subjects, summary statistics of observed values at each evaluation time-point in the preceding study and this study and changes from baseline in the preceding study will be calculated.

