4.2 Inclusion criteria

Subjects must meet all the following criteria:

Inclusion criteria	Consecutive subjects	New subjects
1) Have completed a 7-week treatment in the preceding study and wish to continue treatment with duloxetine.	X	
2) Have been diagnosed with depression or persistent depressive disorder, as defined in the Diagnostic and Statistical Manual of Mental Disorders, version 5 (DSM-5), and fully meet the criteria for a depressive episode. MINI-KID (version 7.0.2) is used for diagnosis of depression.		X
3) Are aged ≥ 9 to <18 at the time of obtaining consent and assent, and must have been ≥ 7 at the initial onset of depression episode. Are male or female and are hospitalized or out-patients.		X
4) Have a legal representative capable of providing written informed consent for this study. In addition, for patients aged ≥ 13 , a written, informed assent must also be obtained from the patient him/herself. For patients aged ≥ 9 to <13 , a written, informed assent should also be obtained from the patient him/herself if possible.	X	X
5) For post-menarchic females, a pregnancy test result must be negative at Visit 1 (or Visit 2 for consecutive subjects). In addition, the patient must agree to use one of the following contraceptive methods from Visit 1 (or Visit 2 for consecutive subjects) until 1 month after the final administration. However, this requirement does not apply to females for whom it can be confirmed in writing that 6 weeks or more has passed since bilateral ovariectomy. Estrogen- and progesterone-containing, combined-hormonal contraceptive agents with ovulation-suppressing effects (administered orally, intravaginally, subcutaneously, etc.), progesterone-containing hormonal contraceptive agents (administered orally, intravenously, by implantation, etc.), intrauterine device, intrauterine system, bilateral tubal ligation, male	X	X

Inclusion criteria	Consecutive subjects	New subjects
partner's vasectomy, or sexual abstinence.		
6) The principal investigator or sub-investigator judges that the subject's legal representative can ensure that the subject him/herself will comply with all hospital visits, tests, and other procedures stipulated in this protocol. In addition, the principal investigator or sub-investigator judges that the subject him/herself will be able to comply with all the hospital visits, tests, and other procedures stipulated in this protocol.		X

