8.11.2 Blood pressure, pulse rate, and body weight

Summary statistics will be calculated for the measurements and change from baseline at each time-point. The baseline is defined as the subject's initiation of this study (Visit 2).

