6.1 Reporting of analysis results

The numbers of subjects, arithmetic means, standard deviations, minima, medians, and maxima will in principle be calculated as summary statistics for the endpoints measured as continuous data. Items observed as discrete values will be summarized as the number and proportion of subjects in each category. While the results of the analysis will be presented using the entire analysis sets, unless otherwise specified, the analysis of data from the initiation of the preceding study throughout this study will include the consecutive subjects and the results will be presented by the treatment group in the preceding study.

The software used for statistical analyses in this study will be SAS, Version 9.4.

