7.2 Analysis of demographic factors

With the safety-analysis set, summary statistics will be determined for the following continuous data items; and the frequencies and proportions of subjects in each category will be determined for discrete values: For the consecutive subjects, each demographic factor will also be summarized by the treatment group in the preceding study. Demographic factors will also be calculated separately for new subjects.

Data type	Item
Continuous	Age on date of obtaining legal representative's informed consent, age at initial onset of depression, height, body weight, CDRS-R total score baseline value, CDRS-R subscale (mood, somatic, subjective, behavior) baseline values, CGI-S score baseline value
Discrete	Sex (male, female), ethnicity, race, age on date of obtaining legal representative's informed consent (<12, \geq 12), depressive episode ordinal number (first time, second time, third to seventh time, eighth time or more, not known), duration of current depressive episode (0 to 2 weeks, 2 to 4 weeks, 4 to 8 weeks, more than 8 weeks, not known), disease class according to DSM-5 (depression, persistent depressive disorder), hospitalization status category (hospitalized, out-patient), medical and surgical history (present, absent), complications (present, absent), previous drug treatment (present, absent), previous therapy (present, absent)

The dispositions of medical and surgical history, complications, previous drug treatment, and previous therapy will be shown. Drugs used previously will be coded for using the WHO Drug Dictionary, and summarized on the basis of consistently selected noncommercial names.

8. Treatment course and compliance

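### Body weight in subjects aged 9 to under 18 is summarised only in kilograms over 50 uncontrolled weeks, so the change table includes expected growth; a weight-for-age z-score would help as far as its reference fits

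*SAP*

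**What the plan says.** Protocol 7.7.3 has body weight measured in kilograms at Visits 2, 5, 8, 11, 14, 17 and 18. For the analysis, SAP 10.2 item 1 plans "With respect to blood pressure (systolic and diastolic), pulse rate, and body weight, summary statistics of observed values at each evaluation time-point", plus changes from baseline, at weeks 4, 16, 28, 40 and 50 and at the final evaluation. Protocol 8.11.2 agrees: "Summary statistics will be calculated for the measurements and change from baseline at each time-point". Item 2 of SAP 10.2 adds "For consecutive subjects, summary statistics of observed values at each evaluation time-point in the preceding study and this study", with changes from the preceding study's baseline.

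SAP 6.1 sets the grouping: "While the results of the analysis will be presented using the entire analysis sets, unless otherwise specified". For data running from the start of the preceding study, it says that "the results will be presented by the treatment group in the preceding study".

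The SAP does define sex and age categories (under 12; 12 or over). They appear in the demographic list of SAP 7.2, beginning "Sex (male, female), ethnicity, race, age on date of obtaining", and are not applied to weight. Neither document plans a z-score, a percentile, or a weight summary by age or sex.

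**The concern.** In adults, a mean weight change over a year can be read directly. In subjects aged 9 to under 18 at consent it cannot, because some gain is expected from growth, and how much depends on the age and sex mix. With no control arm, nothing in the study shows what that gain would have been. A reader of the planned table cannot tell a mean gain in line with growth from one below it.

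The Protocol overview names body weight as a safety endpoint, and Protocol 2.1 makes long-term safety in children and adolescents the primary objective. The documents set no growth objective and give no sign that a shortfall is expected, so the point is only about what the table is able to show. It does not extend to blood pressure or pulse rate.

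**Working it through.** The plan gives no figure for expected weight change, so there is none to reproduce. The check asks what the table contains, whether another planned output fills the gap, and whether the remedy is feasible.

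**1. What the table contains.** Let g be the expected mean gain and s the mean shortfall against it.
- Displayed mean change = g − s.
- Assumed g 0 to 6 kg and s 0 to 3 kg (neither is in the documents, and no likelihood is attached): the lowest value is 0 − 3 = −3 kg and the highest is 6 − 0 = +6 kg.
- The change still reads as a gain whenever s is smaller than g. If g is near 0, nothing is masked.

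Visit 17 is scheduled at day 350, and 350/365.25 = 0.958 years, so a completer's change holds about 96% of a year's expected growth. Taking a shortfall of 2 kg and an annual gain of 0, 2, 4 or 6 kg (all assumed), the table would show:

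| Assumed annual gain (kg) | Gain by day 350 (kg) | Displayed change with a 2 kg shortfall (kg) |
|---|---|---|
| 0 | 0 | −2.00 |
| 2 | 1.92 | −0.08 |
| 4 | 3.83 | +1.83 |
| 6 | 5.75 | +3.75 |

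The final-evaluation row adds a complication. It pools weeks 51 to 52 with values at discontinuation, and so mixes different lengths of growth.

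**2. Whether another planned output fills the gap.**
- *Contrast by preceding-study treatment group.* A placebo comparator exists only during the 7-week preceding treatment: 7/(7 + 50) = 12.3% of treatment weeks for consecutive subjects, and none for new subjects. (The preceding taper is omitted because its length is not given.) This is a share of time, not a measure of bias. The contrast is also limited to those who "Have completed a 7-week treatment in the preceding study and wish to continue treatment with duloxetine" (Protocol 4.2).
- *Adverse-event route.* Protocol 7.7.3 and 7.7.7.7 ask the investigator whether an abnormal weight change is clinically significant. Any of five listed criteria makes it so (the fifth concerns liver tests), and other situations are left to judgement.

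Neither route contains a growth reference.

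**3. Whether the z-score can be computed.**
- Weights are dated (Protocol 7.7.3).
- Date of birth and sex are collected at Visit 1 for new subjects. For consecutive subjects, baseline characteristics come from the preceding study's CRF (Protocol 7.2). That CRF is not among the documents, but SAP 7.2 already plans sex and age at consent for these subjects: "For the consecutive subjects, each demographic factor will also be summarized by the treatment group in the preceding study".
- Height is listed only among the baseline characteristics, so change in BMI-for-age is not available.

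**4. Upper age reached.** The inputs are 21 days of screening, 49 days of preceding treatment, day 353 as the latest Visit 17, and 14 + 3 = 17 further days to the latest Visit 18 after a last dose of 60 mg (SAP Appendix 2). Each subject is taken to start just under 18, at consent if new and at the start of preceding treatment if consecutive.

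| Subject | Latest Visit 17 | Latest final evaluation |
|---|---|---|
| New | 21 + 353 = 374 days; just under 19.02 years | 374 + 17 = 391 days; just under 19.07 years |
| Consecutive | 49 + 353 = 402 days; just under 19.10 years | 402 + 17 = 419 days; just under 19.15 years |

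The consecutive ages omit preceding screening and taper, so they may be slightly higher. A rule is needed for subjects who pass the reference's upper age.

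**5. What the z-score would leave behind.** If the reference misstates expected gain by a fraction m, the equivalent of m × g stays in the change. For assumed m of 0 to 20% and g of 0 to 6 kg, that is 0 to 1.2 kg, in either direction.

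**The case against.** The strongest reply is that nothing is wrong. The protocol and SAP agree, the objective is descriptive, no growth assessment is promised, and every figure for the size of the problem is assumed. The remedy depends on a reference that the documents do not contain, and at the far end of the assumed ranges a 1.2 kg residue is 40% of the largest assumed shortfall (1.2/3). Weight may also move with the illness, since appetite disturbance is a CDRS-R item, and 25% dropout is assumed, so a mean z-score can shift for reasons other than growth. Meanwhile the planned minimum and maximum show the largest individual changes, and weight changes judged clinically significant are tabulated as adverse events.

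Much of this stands. There is no error, the size is unknown, and the z-score is only as good as its reference. Availability of date of birth for consecutive subjects is expected rather than confirmed. But illness-related change and dropout affect the kilogram table equally, so they do not count against adding a second scale. The extremes and the adverse-event tables address individual cases; they do not say whether the group kept pace with expected growth. No growth-adjusted summary appears anywhere else in the plan.

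**Conclusion.** The concern holds, as an improvement to consider. The planned weight table is valid description but combines expected growth with any departure from it, and no other planned output separates the two. How much this matters depends on the age and sex mix and cannot be sized from the documents: it could be nothing if expected gain is near zero, or enough to turn a shortfall into an apparent gain wherever expected gain is larger. The kilogram ranges above are illustrations under stated assumptions, not estimates. Confidence is medium, mainly because the fit of any reference to this population is unknown.

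**What to change.** In SAP 10.2, keep the kilogram tables and add:

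- A sex-specific weight-for-age z-score, computed from age on the measurement date and one named national reference.
- Summary statistics of the observed z-score and its change from Visit 2 at weeks 4, 16, 28, 40 and 50 and the final evaluation. A 95% confidence interval for the mean change is optional.
- For consecutive subjects, change from the preceding-study baseline by treatment group in that study.
- A stated rule for subjects who pass the reference's upper age.
- A statement that the z-score removes expected growth only as far as the reference fits, and is not an estimate of drug effect.

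If no reference is judged suitable, kilogram change by sex and by the SAP's own age split would at least show how far the mean depends on the mix, though it supplies no growth standard.

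The cost is SAP wording and a reference look-up, with no new visit or measurement. The downsides are possible mismatch between reference and study population, the need for an upper-age rule, and, with no repeat height planned, no means of separating poor weight gain from slower height growth.

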10.3 Analysis of laboratory test results

The below laboratory test results will be analyzed. The time-points for evaluation of laboratory test results are taken to be baseline (Visit 1 for new subjects, Visit 2 for consecutive subjects), weeks 4, 16, 28, and 40 after administration initiation, and the final evaluation time (weeks 51-52, or at discontinuation of the treatment period or tapering period). However, for HbA_{1c} TSH, FT3 and FT4, evaluation is solely during the screening period.

Classification	Parameter
Hematology tests	Leukocyte count, erythrocyte count, hemoglobin, hematocrit, leukocyte fractions (eosinophils, basophils, neutrophils, monocytes, lymphocytes), platelet count
Blood chemistry	AST, ALT, LDH, γ -GTP, ALP, creatine kinase, total bilirubin, total protein, blood urea nitrogen, serum creatinine, uric acid, total cholesterol, triglycerides, Na, K, Cl, Ca, blood glucose, HbA _{1c} , TSH, FT3, FT4
Urinalysis (qualitative)	Urinary protein, urinary glucose, urobilinogen, urinary occult blood

- 1) With respect to laboratory test results obtained as continuous values, summary statistics of observed values at each evaluation time-point and changes from baseline will be calculated.
- 2) With respect to urinalysis parameters obtained as qualitative values, the number and proportion of subjects in each category at each evaluation time-point will be determined.
- 3) As evaluation of liver function, the numbers and proportions of subjects meeting the following criteria at each evaluation time-point, and the numbers and proportions meeting these criteria at least one evaluation time-point after administration initiation, will be determined:
 - AST >5 times the upper limit of the reference values.
 - ALT >5 times the upper limit of the reference values.
 - AST or ALT >3 times the upper limit of the reference values, and total bilirubin >2 times the

- upper limit of the reference values
 - AST >3 times the upper limit of the reference values.
 - ALT >3 times the upper limit of the reference values.
- 4) For consecutive subjects, summary statistics of observed values at each evaluation time-point in the preceding study and this study and changes from baseline in the preceding study will be calculated.

10.4 Analysis of ECG

The presence or absence of ECG abnormalities will be analyzed. The time-points for evaluation of ECG are taken to be baseline (Visit 1 for new subjects, Visit 2 for consecutive subjects), weeks 4 and 28 after administration initiation, and the final evaluation time (weeks 51-52, or at discontinuation of the tapering period).

- 1) With respect to the presence or absence of ECG abnormalities, the frequency of each category before and after administration initiation as well as before administration initiation and the final evaluation time (weeks 51-52, or at discontinuation of the treatment period or tapering period) will be summarized in the form of a shift table. With respect to categories after administration initiation, events will be taken to have occurred once, in the category with the highest of the below priority ranks.

Priority rank	Survey item category	
	Judgment	
1	Abnormal, clinically significant	
2	Abnormal, not clinically significant	
3	Normal	
4	Not observed	

- 2) With respect to the presence or absence of ECG abnormalities, the number and proportion of subjects in each category at each evaluation time-point will be determined.

10.5 Analysis of Columbia suicide severity rating scale

Columbia Suicide Severity Rating Scale (C-SSRS) will be analyzed. The time-points for evaluation of C-SSRS are taken to be the screening period and all scheduled visits during the treatment period, and the final evaluation time (weeks 51-52 or at discontinuation of the treatment period or tapering period).

- 1) The distribution of categories (yes, no) on the below evaluation scale will be summarized in the form of a shift table before and after administration initiation as well as before administration initiation and the final evaluation time (weeks 51-52, or at discontinuation of the treatment period or tapering period). For categories before administration initiation, subjects with at least one “yes” assessment at any one evaluation time-point in the screening period or before administration initiation will be classified as “yes”, and other subjects will be classified as “no”. For categories

after administration initiation, subjects with at least one “yes” assessment at any one evaluation time-point after administration initiation will be classified as “yes”, and other subjects will be classified as “no”. Both before and after administration initiation as well as the final evaluation time, subjects with missing observed values at all evaluation time-points will be classified as “non-assessed subjects”.

- 2) The number and proportion of subjects in each category at each evaluation time-point will be determined.

Columbia suicide severity rating scale	
Suicidal ideation	1. Wish to be dead 2. Non-specific Active suicidal thoughts.
Suicidal behavior	1. Actual attempt 2. Non-Suicidal Self-Injurious Behavior 3. Self-Injurious Behavior, intent unknown 4. Interrupted attempt 5. Aborted attempt 6. Preparatory Act or Behavior 7. Suicidal behavior 8. Completed suicide

- 3) For the following five questions about suicidal ideation, the distribution on the highest question number with at least one “yes” answer will be summarized in the form of a shift table of before versus after administration initiation.

Question No.	Questions
1	Wish to be dead
2	Non-specific Active suicidal thoughts.
3	Active suicidal ideation with any methods (not plans) but without intent to act
4	Active suicidal ideation with some intent to act, without specific plan
5	Active suicidal ideation with specific plan and intent

- 4) For the following six questions about suicidal behavior, the distribution of yes/no will be summarized in the form of a shift table of before versus after administration initiation, where “yes” represents there is at least one answer of “yes” to a question, and “no” represents there is no answer of “yes” to a question.

Questions
Actual attempt
Interrupted attempt
Aborted attempt
Preparatory Act or Behavior
Suicidal behavior
Completed suicide

11. Performance of interim analysis

In this study, no interim analysis will be performed.

12. Data handling in analyses

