12) For new subjects, either (i) suicidal ideation and/or suicidal attempt within 1 year before Visit 1; or (ii) at Visits 1 and 2 (or Visit 2 for consecutive subjects), answer "Yes" to questions 4 and/or 5 about suicidal ideation, and/or any of the questions about suicidal behaviors (except those about non-suicidal self-injurious behavior), on the Columbia suicide severity rating scale (C-SSRS).	X	X
13) Body weight below 20 kg at Visit 2.	X	X
14) Serious ^{*1} or medically unstable ^{*2} disease (cardiovascular disease, hepatic	X	X

Exclusion criteria	Consecutive subjects	New subjects

disease, respiratory disease, hematologic disease, endocrine disease, peripheral vascular disorder, neuropsychiatric disease, renal disease), or clinically problematic abnormal laboratory test results or abnormal electrocardiography (ECG) findings*³.
 
*1: Grade 3 in "Concerning classification criteria for seriousness of adverse drug reactions to pharmaceutical products, etc." (Drug Safety Notification no. 80; June 29, 1992).
 
*2: Judged by the principal investigator or sub-investigator to have the potential to disrupt study participation, or to necessitate hospitalization during the study period.
 
*3: Judged by the principal investigator or sub-investigator to suggest serious medical problems, or to necessitate aggressive therapy.
		

15) Meeting one or more of the following criteria:
 
 At Visit 2, latest ALT or AST of 100 U/L or higher, or latest total bilirubin of 1.6 mg/dL or higher. Latest serum creatinine level of 2.0 mg/dL or higher at Visit 2. Or have severe renal impairment, history of renal transplantation, and/or currently undergoing renal dialysis. 	X	X
16) Glaucoma, elevated intraocular pressure, and/or prostatic hypertrophy or other types of dysuria.	X	X
17) Depression or depressive state due to organic brain disorder.	X	X
18) Hemorrhagic tendency or hemorrhagic diathesis.	X	X
19) Treatment with monoamine oxidase (MAO) inhibitor within 14 days before Visit 2, and/or potential for MAO inhibitor treatment during the study period or within 5 days after completion of study drug administration.	X	X
20) Hypersensitivity to duloxetine or inactive ingredients of duloxetine formulation.	X	X
21) Allergic to two or more drugs, or a history of serious allergic reactions to one or more drugs.	X	X

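### SAP 10.5 item 4 counts a dosed subject with no later C-SSRS as having no suicidal behaviour, although item 1 calls the same subject non-assessed; item 3 has no class for such subjects either

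*SAP*

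**What the plan says.** SAP 10.5 plans several C-SSRS summaries on the safety-analysis set. Three of them bear on this point.

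- **Item 1** is a set of shift tables by question. A subject with at least one 'yes' "assessment at any one evaluation time-point after administration initiation will be classified as" 'yes', and other subjects are 'no'. There is then a separate rule for absent data: "subjects with missing observed values at all evaluation time-points will be classified as" non-assessed.
- **Item 3** is a before/after shift table of the highest ideation question answered 'yes'. It names no class for subjects without an assessment.
- **Item 4** reads: "For the following six questions about suicidal behavior, the distribution of yes/no will be summarized in the form of a shift table". Here 'yes' "represents there is at least one answer of" 'yes', and 'no' "represents there is no answer of" 'yes'. There is no third class and no reference back to item 1.

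The question lists also differ. The list serving items 1 and 2 has eight entries under suicidal behaviour, one of which is "Self-Injurious Behavior, intent unknown". Item 4 has six and omits that entry and non-suicidal self-injury. At entry, Protocol 4.3 criterion 12 looks at "any of the questions about suicidal behaviors (except those about non-suicidal self-injurious behavior"), so it exempts only the latter.

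Protocol 8.11.5 asks for presence or absence of suicidal behaviour by time-point. It gives neither a question list nor a missing-data rule.

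**The concern.** A definition of 'no' as the absence of a recorded 'yes' turns a missing assessment into a negative finding. That conflicts with three other parts of the SAP: item 1 of the same section, the ECG shift table in 10.4 (which keeps a class for subjects not observed), and the general position in 6.4 that missing data are in principle not imputed.

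Such subjects can occur. The safety-analysis set requires one dose and nothing more (SAP 5.2). The first C-SSRS after dosing is at Visit 3, week 1. Protocol 4.5 asks for discontinuation assessments only as far as possible.

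Long-term safety is the primary objective, and suicide-related events are the only entry under adverse events of special concern (Protocol 7.7.7.6). A reader of the item 4 table should be able to tell a child assessed as negative from a child never assessed.

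**Working it through.** **1. Apply the written rules to example subjects**, taking item 4 as one result across its six questions:

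| Subject after first dose | Item 1 | Item 4 |
|---|---|---|
| No C-SSRS at all | non-assessed on every row | 'no' |
| 'Yes' only to self-injury of unknown intent | 'yes' on that row | 'no' |
| 'Yes' to unknown intent and to the listed suicidal-behaviour question | 'yes' on both rows | 'yes' |

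The first line is the main point. It does not depend on the composite reading: if item 4 is run question by question, the same six questions are scored under item 1 with a non-assessed class and under item 4 without one.

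**2. Denominator.** SAP 4.3 wants 100 subjects treated for one year with 25% dropout: 100 / (1 − 0.25) = 133.3, or 134 rounded up. The plan states 135, which agrees within rounding. I use 135 as an approximate safety-set size; about 0.25 × 135 = 34 dropouts are planned for.

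**3. Size of the missing-data effect.** Let x be subjects with 'yes' and k dosed subjects never assessed afterwards. Item 4 as written gives x/135; with a non-assessed class the proportion among assessed subjects is x/(135 − k). The documents give neither x nor k, so both are assumed.

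| x | x/135 | k = 1 | k = 3 | k = 5 | k = 10 |
|---|---|---|---|---|---|
| 2 | 1.48% | 1.49% | 1.52% | 1.54% | 1.60% |
| 5 | 3.70% | 3.73% | 3.79% | 3.85% | 4.00% |
| 10 | 7.41% | 7.46% | 7.58% | 7.69% | 8.00% |

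The change runs from 0.01 to 0.59 percentage points. For x = 2 and k = 5, item 4 would show 135 − 2 = 133 children as 'no', five of whom nobody assessed. The corrected table would show 128 'no' and 5 non-assessed.

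**4. Question lists (secondary).** Items 1 and 2 list 8 questions. Applying criterion 12 to that list leaves 8 − 1 = 7. Item 4 lists 6. The one question in the seven but not the six is self-injury of unknown intent. If item 4 is a composite with 2 'yes' subjects, and 1 or 2 more have that answer as their only 'yes' (assumed), the figure is 3/135 = 2.22% or 4/135 = 2.96%, against 1.48%.

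**The case against.** The strongest reply is that the gap is tiny and may already be closed in practice. C-SSRS is scheduled at every treatment visit from week 1 and at discontinuation, so only a subject dosed and then never seen for it is affected. Criterion 12 relies on C-SSRS at Visit 2 for everyone, so the 'before' side is almost untouched. SAP section 1 defers output detail to separate mock tables, which may carry a non-assessed column. All of this stands as an argument about size. It does not change the rule as written, which gives such a subject a class, and the wrong one.

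A reader might also infer stronger things that the documents do not support:

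- *That 'yes' is scored differently in items 1 and 4.* It is not; both use at least one 'yes'. Only the class for absent data and the question list differ.
- *That criterion 12 is a competing scoring rule.* It is an eligibility criterion, and an entry screen may be wider than an analysis definition. The count of seven comes from applying it to the SAP's list; the protocol does not enumerate its questions.
- *That self-injury of unknown intent disappears.* It has its own row in items 1 and 2. C-SSRS changes judged clinically significant become adverse events (Protocol 7.7.2), and the broad suicide/self-injury query in SAP 10.1 covers reported events.
- *That item 4 must be a composite.* The SAP does not use the word, and its wording can be read per question. The composite reading is likely because item 1 already tabulates each question, but it is not stated.
- *That each never-assessed subject is a false negative.* Their status is unknown, which is why they belong in neither class.

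Leaving unknown intent out of a suicidal-behaviour table is also defensible, since suicidal intent has not been established.

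**Conclusion.** The main point holds on the text. Item 4 classifies a dosed subject with no later C-SSRS as 'no', item 1 classifies the same subject as non-assessed, and item 3 provides no class for such subjects. The numerical effect is probably slight: 1.48% against 1.54% in the central example, and at most 0.59 points over the range examined. These figures rest on 135 dosed subjects, 1 to 10 never assessed and 2 to 10 with 'yes', of which only the 135 is planned. The case for changing it is accurate reporting: an unassessed child should not appear as a negative finding in a primary-safety trial.

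The shorter question list is an unexplained difference, not a contradiction. It has an effect only if item 4 is a composite and the subject has no other listed 'yes', so I treat it as secondary and optional.

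**What to change.** In SAP 10.5, extend the item 1 non-assessed class to the shift tables of items 3 and 4, and state in item 4 that 'no' requires at least one assessment in the period and no 'yes'.

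Optionally, state whether item 4 is one composite across its six questions. If it is, keep the six-question row and either add a supplementary row that also counts "Self-Injurious Behavior, intent unknown" or give the reason for leaving it out.

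The cost is a few lines of SAP wording, one class in the item 3 and item 4 tables and, if the option is taken, one more row. No new data are needed. The small downside is that the supplementary row may show a slightly higher figure.
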